### **8.6 Pharmacokinetics**

#### **8.6.1 Blood Collection for Plasma Selumetinib and Serum Pembrolizumab**

Sample collection, storage, and shipment instructions for pharmacokinetic samples will be provided in the operations/laboratory manual.

Pharmacokinetic samples should be drawn according to the PK collection schedule for all participants. The exact time of sample collection and time of administration of selumetinib and pembrolizumab will be recorded. Pharmacokinetic samples should be drawn according to the PK collection schedule for all participants.

Blood samples for determination of plasma concentrations of selumetinib and N-desmethyl selumetinib. Other metabolites (eg, selumetinib amide) may also be determined. Plasma samples for selumetinib and N-desmethyl selumetinib will be obtained from consenting participants. Serial plasma samples for PK analysis of selumetinib and N-desmethyl selumetinib will be collected C1D1: Pre-dose at time 0 and post-dose at 1 ( $\pm$  10 minutes), 2 ( $\pm$  10 minutes), 4 ( $\pm$  10 minutes), 6 ( $\pm$  10 minutes), and 1 sample any time between 8 and 12 hours (prior to PM dosing for BID regimen). Additional samples will be collected at C2D1, C2D14, C5D1 and C5D14 at time 0 pre-dose ( $\pm$  10 minutes). Morning dose(s) should be withheld until after PK (pre-dose) sample has been drawn.

Blood samples for determination of serum concentrations of pembrolizumab will be obtained from consenting participants. Serial serum samples for PK analysis of pembrolizumab will be collected at pre-dose (trough) PK and samples within 24 hours before infusion at Cycles 1, 2, 3, 5, 8, and every 4 cycles thereafter.

If ongoing PK sampling is deemed to be unnecessary by the Sponsor, it may be reduced or discontinued.

## **8.7 Pharmacodynamics**

Pharmacodynamic parameters will not be evaluated in this study.

## **8.8 Future Biomedical Research Sample Collection**

[figure not shown]
If the participant signs the future biomedical research consent, the following specimens will be obtained as part of future biomedical research:

- Leftover specimens listed in Section 8.10, Biomarkers

## **8.9 Planned Genetic Analysis Sample Collection**

The planned genetic analysis sample should be drawn for planned analysis of the association between genetic variants in DNA and drug response. This sample will not be collected at the site if there is either a local law or regulation prohibiting collection, or if the IRB/IEC does not approve the collection of the sample for these purposes. If the sample is collected, leftover extracted DNA will be stored for future biomedical research if the participant signs the future biomedical research consent. If the planned genetic analysis is not approved, but future biomedical research is approved and consent is given, this sample will be collected for the purpose of future biomedical research.

CCI

### 8.10.1 Screening

Approximately 28 days prior to treatment allocation, potential participants will be evaluated to determine that they fulfill the entry requirements (with the exception of MSI status, ophthalmologic examination, and MUGA/ECHO will be evaluated within 42 days) as set forth in Sections 5.1 and 5.2. Screening procedures may be repeated after consultation with the Sponsor. Written consent must be obtained prior to performing any protocol-specific procedure. Results of a test performed prior to the participant signing consent as part of routine management are acceptable in lieu of a screening test if performed within the specified time frame. Screening procedures are to be completed within 28 days prior to the first dose of study intervention except for the following:

- Laboratory tests are to be performed within 3 days prior to the first dose of study intervention. An exception is hepatitis testing, which may be done up to 28 days prior to the first dose of study intervention.
- Evaluation of ECOG is to be performed within 3 days prior to the first dose of study intervention.

- For women of reproductive potential, a urine or serum pregnancy test will be performed within 72 hours prior to the first dose of study intervention. If urine pregnancy results cannot be confirmed as negative, a serum pregnancy test will be required (performed by the local study site laboratory).
- Archival tumor sample collection is not required to be obtained within 28 days prior to the first dose of study intervention. Newly obtained tumor tissue may be obtained within 90 days of study intervention initiation.

#### **8.10.2 Treatment Period**

Visit requirements are outlined in Section 1.3. Specific procedure-related details are provided above in Section 8.

#### **8.10.3 Discontinued Participants Continuing to be Monitored in the Study**

The Discontinuation Visit should occur at the time study intervention is discontinued for any reason. If the Discontinuation Visit occurs 30 days from the last dose of study intervention, at the time of the mandatory Safety Follow-up Visit, the Discontinuation Visit procedures and any additional Safety Follow-up procedures should be performed. Visit requirements are outlined in Section 1.3. Additional details regarding participant withdrawal and discontinuation are presented in Section 7.

#### **8.10.4 Safety Follow-up Visit**

The mandatory Safety Follow-up Visit should be conducted approximately 30 days after the last dose of study intervention or before the initiation of a new anticancer treatment, whichever comes first.

All AEs that occur prior to the Safety Follow-up Visit should be recorded (up to 30 days following end of treatment). Participants with an AE of Grade >1 will be followed until the resolution of the AE to Grade 0 to 1 or until the beginning of a new anticancer therapy, whichever occurs first. SAEs that occur within 30 days (90 days following administration of pembrolizumab) of the end of treatment or before initiation of a new anticancer treatment should also be followed and recorded.

#### **8.10.5 Imaging Follow-up Visit**

Participants who discontinue study intervention for reasons other than verified PD should continue with imaging assessments per the protocol-defined schedule until: (1) PD is verified or further confirmed by the investigator, (2) initiation of a new anti-cancer treatment, (3) death, (4) withdrawal of consent, or (5) study conclusion or early termination, whichever occurs first.

### 8.10.6 Survival Follow-up Visit

Participants who experience confirmed disease progression or start a new anticancer therapy will move into the Survival Follow-Up Phase and should be contacted by telephone every 12 weeks to assess for survival status until death, withdrawal of consent, or the end of the study, whichever occurs first.

The Sponsor may request survival status be assessed at additional time points during the study. For example, these additional time points may be requested prior to an efficacy interim analysis, and/or final analysis. All participants who are not known to have died prior to the request for these additional survival status time points will be contacted at that time.

### 8.10.7 Poststudy

Participants will be required to return to clinic approximately 14 days after the last dose of study intervention for the poststudy visit. If the poststudy visit occurs less than 14 days after the last dose of study intervention, a subsequent follow-up telephone call should be made at 14 days post the last dose of study intervention to determine if any AEs have occurred since the poststudy clinic visit.

## 9 STATISTICAL ANALYSIS PLAN

### 9.1 Statistical Analysis Plan Summary

This section outlines the statistical analysis strategies and procedures for the primary and secondary analyses of the study. Exploratory and other nonconfirmatory analyses will be outlined in a separate supplemental Statistical Analysis Plan (sSAP).

If, after the study has begun, changes are made to primary and/or secondary objectives, or the statistical methods related to those objectives, then the protocol will be amended (consistent with ICH Guideline E9). Changes to exploratory or other nonconfirmatory analyses made after the protocol has been finalized, but prior to the conduct of any analyses, will be documented in the sSAP as needed and referenced in the Clinical Study Report (CSR) for the study. Post hoc exploratory analyses will be clearly identified in the CSR.

Study Design Overview	Phase 1b trial of selumetinib in combination with pembrolizumab in participants with histologically or cytologically confirmed diagnosis of metastatic/advanced solid tumor. The study applies an mTPI design for dose escalation and confirmation of RP2D.
Treatment Assignment	Participants will be allocated centrally through IVRS/IWRS to selumetinib in combination with pembrolizumab.
Analysis Populations	Safety (Primary): All-Participants-as-Treated (APaT) PK (Secondary): Per-Protocol (PP) Efficacy (Exploratory): Full Analysis Set

Primary Endpoint(s)	

• Dose-limiting toxicities (DLTs)

• Adverse events (AEs)

• Study drug discontinuations due to an AE

Secondary Endpoints	Pharmacokinetic parameters including area under the curve (AUC), minimum concentration ( $C_{min}$ ) and maximum concentration ( $C_{max}$ )
Statistical Methods for Efficacy/ Immunogenicity/ Pharmacokinetic Analyses	Efficacy analyses are documented in the sSAP. PK parameters of study medicines will be summarized by planned visit and time for each dose separately.
Statistical Methods for Safety Analyses	Summary statistics will be provided for the safety endpoints. The pool-adjacent-violators-algorithm [Ji Y, Li Y, Bekele BN 2007] will be used to estimate the DLT rates across doses. The estimate of the DLT rate among participants treated at RP2D of selumetinib (MK-5618) in combination with pembrolizumab (MK-3475) and the 80% Bayesian credible intervals for the estimate will be provided for each treatment arm.
Interim Analyses	An interim analysis may be conducted to enable future trial planning at the Sponsor's discretion and data will be examined on a continuous basis to allow for dose-finding decisions.
Multiplicity	No multiplicity adjustment is planned in this Phase 1b trial.
Sample Size and Power	The overall sample size for this study depends on the observed DLT profiles of selumetinib in combination with pembrolizumab. A target sample size of 50 participants will be used for study planning purposes.

## 9.2 Responsibility for Analyses/In-house Blinding

The statistical analyses of the data obtained from this study will be the responsibility of the Clinical Biostatistics department of the Sponsor.

The trial is open-label, ie, participants, investigators, and Sponsor personnel will be aware of participant treatment assignment after each participant is enrolled and treatment is assigned. Allocation to treatment will not be randomized.

## 9.3 Hypotheses/Estimation

There is no hypothesis testing in this study. Objectives of the study are outlined in Section 3 – Hypotheses, Objectives, and Endpoints.

## 9.4 Analysis Endpoints

### 9.4.1 Pharmacokinetics/Efficacy Endpoints

Pharmacokinetic endpoint is secondary [REDACTED] for selumetinib [REDACTED]. [REDACTED] Pharmacokinetic profile of selumetinib [REDACTED] will be characterized. The PK concentrations of selumetinib (and its metabolites) [REDACTED] [REDACTED] will be used to derive PK parameters of the agents (such as  $C_{max}$ , AUC and/or  $C_{min}$ ). Furthermore, the results of these analyses will be potentially used in conjunction with the pharmacodynamics, safety, and exploratory endpoint data to help assess future dosing strategies for selumetinib.

[REDACTED]

### 9.4.2 Safety Endpoints

The primary safety endpoint is the incidence of DLTs. In addition, safety and tolerability will be assessed by clinical review of all relevant parameters including AEs, laboratory tests, and vital signs.

A description of safety measures is provided in Section 8.3 – Safety Assessments.

## 9.5 Analysis Populations

### 9.5.1 Safety Analysis Populations

The All-Participants-as-Treated (APaT) population will be used for the analysis of safety data in this study. The APaT population consists of all participants who received at least 1 dose of study treatment.

The DLT evaluable population includes APaT participants that meet the criteria for DLT evaluability (eg, finished Cycle 1 without a DLT or experienced a DLT in Cycle 1). See Section 6.6.2.2 for details.

At least 1 laboratory or vital sign measurement obtained subsequent to at least 1 dose of study treatment is required for inclusion in the analysis of each specific parameter. To assess change from baseline, a baseline measurement is also required.

### 9.5.2 Pharmacokinetic Analysis Populations

The Per-Protocol (PP) population will be used for the analysis of PK and target engagement data in this study. The PP population consists of the subset of participants who complied with

the protocol sufficiently to ensure that their data will be likely to exhibit the effects of treatment, according to the underlying scientific model. Compliance includes such considerations as exposure to treatment, availability of measurements, and the absence of major protocol violations. Any participants or data values excluded from the analyses will be identified, along with the reasons for exclusion, in the CSR. At the end of the study, all participants who were compliant with the study procedures and have available data from at least 1 treatment will be included in the PP analysis dataset.

### **9.5.3 Efficacy Analysis Populations**

The Full Analysis Set population will be used for the analyses of efficacy data in this study. It consists of all participants with a baseline scan that demonstrated measurable disease by the investigator's assessment, and who were administered at least 1 dose of study medicine.

## **9.6 Statistical Methods**

This section describes the statistical methods that address the primary and secondary objectives. Methods related to exploratory endpoints will be described in the sSAP.

### **9.6.1 Statistical Methods for Efficacy Analysis**

The statistical methods for efficacy analyses will be documented in the sSAP.

### **9.6.2 Statistical Methods for Safety Analysis**

Safety and tolerability will be assessed by clinical review of all relevant parameters including AEs, SAEs, laboratory tests, vital signs, ECG measurements, and physical examinations.

Adverse events will be summarized by counts and frequencies for each dose level. Laboratory tests, vital signs, and other safety endpoints will be summarized.

Dose limiting toxicities will be listed and summarized by dose level. The isotonic regression with pool-adjacent-violators-algorithm [Ji Y, Li Y, Bekele BN 2007], which forces the DLT rate estimates to be nondecreasing with increasing dose levels and pools adjacent violators for weighted estimates by sample size, will be used to estimate the DLT rates across doses in each treatment arm. The estimate of the DLT rate among participants treated at the RP2D and the 80% Bayesian credible interval based on a prior distribution of Beta (1,1) for the estimate will be provided.

### **9.6.3 Summaries of Baseline Characteristics, Demographics, and Other Analysis**

#### **9.6.3.1 Demographic and Baseline Characteristics**

Demographic variables, baseline characteristics, primary and secondary diagnoses, and prior and concomitant therapies will be summarized.

### **9.6.3.2 Pharmacokinetic and Pharmacodynamic Modeling Analysis**

Pharmacokinetic parameters of study medicines will be summarized by planned visit and time for each dose separately.

### **9.7 Interim Analyses**

An interim analysis may be conducted to enable future trial planning at the Sponsor's discretion and data will be examined on a continuous basis to allow for dose finding decisions.

### **9.8 Multiplicity**

There will be no multiplicity control in this study.

### **9.9 Sample Size and Power Calculations**

With a maximum sample size of 14 at each dose level, the overall sample size for this Phase 1 trial is expected to be approximately 50. The maximum overall sample size is 84. The actual sample size depends on the safety profiles and number of doses studied.

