### Number of Participants:

Approximately 50 participants will be enrolled in this dose escalation study, as described in Section 9; the overall sample size will be 84 participants maximum for this dose escalation study.

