### **4.3 Justification for Dose**

#### **4.3.1 Starting Dose for This Study**

##### **4.3.1.1 Rationale for Starting and Maximum Dose of Selumetinib**

The RP2D for selumetinib as monotherapy is 75 mg PO BID, administered continuously. In this study, the starting dose of selumetinib will be 50 mg oral BID dosed intermittently for the first 14 days of each 21-day cycle. The dose will be escalated, in 25-mg increments, to above 200 mg (up to 300 mg) oral BID per the mTPI rule, maintaining the intermittent schedule. Outcomes of phase II trial of selumetinib propose that enhanced inhibition of MEK

is associated with a greater clinical response, but MEK inhibition also causes dose dependent AEs. Thus, intermittent dosing might have better results than continuous administration. Preclinical studies have demonstrated that intermittent dosing may delay the development of acquired resistance [Faghfuri, E., et al 2018] [Xue, Y., et al 2017].

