#### 4.3.1.2 Rationale for Dose Interval and Escalation Increments

Doses of selumetinib will start at 50 mg BID, below the monotherapy RP2D dose for selumetinib of 75 mg BID. Dose escalation increments for selumetinib in combination with pembrolizumab will be to 75 mg (50% increase) initially, to the monotherapy RP2D for selumetinib, and then 33% or lower afterwards in increments of 25 mg.

- Starting Dose (Dose Level [DL] 1): MK-5618 50 mg (oral) twice daily (BID), 2 weeks on/1 week off + MK-3475 200 mg IV every 3 weeks (Q3W)
- Escalation Dose (DL2): MK-5618 75 mg (oral) BID, 2 weeks on/1 week off + MK-3475 200 mg IV Q3W
- Escalation Dose (DL3): MK-5618 100 mg (oral) BID, 2 weeks on/1 week off + MK-3475 200 mg IV Q3W
- Escalation Dose (DL4): MK-5618 125 mg (oral) BID, 2 weeks on/1 week off + MK-3475 200 mg IV Q3W
- Escalation Dose (DL5): MK-5618 150 mg (oral) BID, 2 weeks on/1 week off + MK-3475 200 mg IV Q3W
- Escalation Dose (DL6): MK-5618 200 mg (oral) BID, 2 weeks on/1 week off + MK-3475 200 mg IV Q3W
- Escalation Dose (DL7 onwards): MK-5618 above 200 mg (up to 300 mg; oral) BID, 2 weeks on/1 week off + MK-3475 200 mg IV Q3W

This Dose Escalation study will follow the mTPI method (Section 4.3.1.4) to identify the preliminary RP2D of selumetinib used in combination with pembrolizumab.

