When adding participants to a dose level in response to a “stay” decision, the number of additional participants to be enrolled is capped to minimize the exposure to a dose that may be unacceptably toxic (denoted as DU in [Table 1](#)). Secondly, to determine how many more participants can be enrolled at the dose level, one can count steps in diagonal direction (down and to the right) from the current cell to the first cell marked DU. For example, if 1 of 3 participants have experienced a DLT at a given dose level, no more than an additional 3 participants should be enrolled at this dose level until additional DLT data are available. This is because this dose level would be considered unacceptably toxic if all 3 of the additional participants experience a DLT (ie, 4/6 participants with DLT in [Table 1](#)). The same principles will be applied whether 3, 4, 5, or 6 participants are initially enrolled at that dose level.

A D or DU decision at the lowest dose level will stop the trial. An E decision at the highest dose level will result in staying at that level.

Dose finding will end after 14 participants have been enrolled at any of the tested doses and the decision is to stay at the current dose. After 14 participants have been enrolled at any of the tested doses, dose finding will stop if the mTPI table indicates “S” for staying at current dose. Otherwise, up to 14 new participants may be enrolled at a lower dose if “D” or “DU” is indicated, or at a higher dose if “E” is indicated.

The pool-adjacent-violators-algorithm [Ji, Y. 2013] will be used to estimate the DLT rates across doses. The dose with an estimated DLT rate closest to 30% will be treated as a preliminary MTD. However, the totality of the data will be considered before deciding on the dose(s) to carry forward to Part 2, and the escalation schedule may be adjusted based on PD, PK, and safety data emerging throughout the trial.

Note that although 30% was the target toxicity rate used to generate the guidelines in [Table 1](#), the observed rates of participants with DLTs at the MTD may be slightly above or below 30%).

Table 1 Dose-finding Rules per mTPI Design

Number of Participants with at least 1 DLT	Number of Participants Evaluable for DLT at Current Dose											
	3	4	5	6	7	8	9	10	11	12	13	14
0	E	E	E	E	E	E	E	E	E	E	E	E
1	S	S	S	E	E	E	E	E	E	E	E	E
2	D	S	S	S	S	S	S	S	E	E	E	E
3	DU	DU	D	S	S	S	S	S	S	S	S	S
4		DU	DU	DU	D	D	S	S	S	S	S	S
5			DU	DU	DU	DU	DU	D	S	S	S	S
6				DU	DU	DU	DU	DU	DU	D	S	S

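### Does the dose-escalation maximum of 84 conflict with seven listed dose levels at up to 14 participants each?

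*Combined protocol and SAP*

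**What the plan says.** Section 9.9 opens with the limit per level, "With a maximum sample size of 14 at each dose level", gives an expected total of about 50, and then states: "The maximum overall sample size is 84". It adds that the actual size will depend on the safety findings and on how many doses are studied. The synopsis (Section 1.1, Number of Participants) repeats the ceiling: "the overall sample size will be 84 participants maximum for this dose escalation study".

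The dose levels are in Section 4.3.1.2. DL1 to DL6 are fixed doses, and the last entry is open-ended: "Escalation Dose (DL7 onwards): MK-5618 above 200 mg (up to 300 mg; oral) BID". Section 4.3.1.1 describes the range this way: "The dose will be escalated, in 25-mg increments, to above 200 mg (up to 300 mg) oral BID per the mTPI rule".

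Section 4.3.1.4 holds the stopping rules. One is "Dose finding will end after 14 participants have been enrolled at any of the tested doses and the decision is to stay". If Table 1 gives another decision at 14, the text goes on: "Otherwise, up to 14 new participants may be enrolled at a lower dose", or at a higher one if the decision is to escalate. A D or DU decision at the lowest level stops the trial. The dose is then chosen by pooled (isotonic) estimates: "The dose with an estimated DLT rate closest to 30% will be treated as a preliminary MTD". None of these rules refers to 84.

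**The concern.** The number 84 is exactly six times 14, and the plan lists at least seven levels. A reader who takes 84 as a derived total will conclude that one level was left out. A reader who takes it as a cap will look in Section 4.3.1.4 for the point at which dose finding ends on reaching it, and will not find one. Section 5.6 also replaces nonevaluable participants without counting them in the DLT cohort, so it is unclear whether 84 counts enrolled or DLT-evaluable participants.

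If the per-level rule could routinely carry the trial past its stated maximum, two things would be at stake. The ceiling given to sites and ethics committees would be unreliable, and dose finding could be cut off before an MTD had been identified.

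**Working it through.** **1. The stated figures.** The plan's 84 equals 14 x 6; that this is its source is an inference. Seven levels give 14 x 7 = 98, which is 98 - 84 = 14 more (14/84 = 16.7%). If the open-ended last entry were split into 25-mg steps from 225 to 300 mg, there would be 6 + 4 = 10 levels and 14 x 10 = 140. That is an assumption. The list already departs from 25 mg between DL5 (150 mg) and DL6 (200 mg), a discrepancy in step size that the sponsor must reconcile separately.

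**2. Can a level fill to 14 and still escalate?** Yes. Rebuilding Table 1 from the stated Beta(1,1) prior, 30% target and epsilon of 0.03, with an assumed 0.95 cut-off for DU, matches its legible cells. The path 1/3 = S, 2/6 = S, 2/9 = S, 2/14 = E respects the diagonal limits: three more from 1/3 (4/6 = DU), three more from 2/6 (5/9 = DU), and five more from 2/9, where no DU cell is met before the edge of the table. On direct ascent 2/14 is the only full cell that gives E. The written per-level rules therefore do not exclude 98.

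**3. How likely is it?** For that path, with DLT probability p at the level:

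3p(1-p)² x 3p(1-p)² x (1-p)³ x (1-p)⁵ = 9p²(1-p)¹².

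This is largest at p = 2/14 = 1/7, where it is 9 x (1/49) x (6/7)¹² = 0.1837 x 0.1573 = 0.029. Six successive levels filled this way have probability at most 0.029⁶, about 6 in 10¹⁰. Other routes exist, including returns to a lower dose, so simulation is the better guide.

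**4. Simulated totals.** All runs use Table 1, the diagonal limits, at most 14 per level and first cohorts of 3 or 6. DLT curves and the rules for revisiting a dose are assumed, because the plan gives neither.

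| Set | Levels | Runs | Above 84 | Largest total |
|---|---|---|---|---|
| Nine curves, 10,000 runs x 2 cohort sizes | 7 | 180,000 | 0 | 82 |
| Same curves, interpolated | 10 | 180,000 | 151 (0.08%) | 100 |
| Separate larger set | 7 | 360,000 | 1 | not reported |
| Separately programmed, five curves, 3,000 runs x 2 cohort sizes | 7 | 30,000 | 0 | 74 |
| Separately programmed, one curve, cohorts of 6 | 10 | 3,000 | about 0.3% | 92 |

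In the first set the mean total was 19.7 to 49.4, depending on the curve and cohort size. In the second, the worst single scenario passed 84 in 43 of 10,000 runs (0.43%).

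**5. Replacements.** These totals count DLT-evaluable participants. The plan gives no nonevaluable rate. If it were 10% or 20%, the highest seven-level mean would become 49.4/0.9 = 54.9 or 49.4/0.8 = 61.8 enrolled. The mean reaches 84 only at a rate of 1 - 49.4/84 = 41%. An extreme run is different: 82/0.9 = 91, so there the cap would bind if it counts enrolled participants.

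**6. What happens at the cap.** Enrolment stops at 84. The isotonic estimate in Sections 4.3.1.4 and 9.6.2 uses whatever data exist at each dose, and the dose closest to 30% is selected by the same rule. The selected dose might then hold fewer than 14 participants, which is the ordinary price of any overall cap.

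**The case for a change.** The strongest case for a change is that 84 is unclear on either reading. As a total it matches six levels, a count the plan never states. As a cap it has no counterpart in the section that governs dose finding, and its unit is not given. One sentence would settle both, at almost no cost. It could also say that 14 is cumulative per dose, since the wording about new participants could be read as a fresh allowance.

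Part of this stands. The derivation and the unit are absent, and Section 4.3.1.4 does not repeat the limit. The rest does not carry. Both places that give 84 call it a maximum, and a maximum below 14 times the number of levels contradicts nothing. Because the last dose entry is open-ended and Section 4.1 allows other levels to be explored, there is no fixed product to compute. A fixed overall ceiling is a sensible way to limit such a design. Restating the maximum as 98 would raise the stated ceiling to cover an event that practically does not occur, and 98 would itself assume a single level above 200 mg. The cumulative reading of 14 already follows from Section 9.9 and from Table 1, which has no column beyond 14.

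**Conclusion.** No figure is shown to be wrong, and no change is needed. The six-level origin of 84 is a guess, and the plan's own words make it an overall enrolment limit that sits alongside 14 per level. What is missing is a detail of operation that the trial team would fill in the same way: stop at 84 and apply the planned isotonic rule. With seven levels the chance of needing it was between zero and about 3 in a million in the larger simulation sets (0 of 180,000; 1 of 360,000). With ten assumed levels it was about 0.1% on average over the nine curves, at most 0.43% in any one of their scenarios, and about 0.3% in the separately programmed ten-level check. These rates depend on assumed DLT curves and revisit rules and exclude replacements. The consistency of the text does not depend on them. The planning size of 50, the Table 1 decisions and the selection of the preliminary MTD are the same with or without the extra sentence.
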